#### **13.1.4.2 Clinical Laboratory Evaluations**

Descriptive summaries (mean, SD, median, minimum, and maximum) of actual (absolute) values and changes from baseline values will be presented for clinical laboratory values for each time point.

The number of subjects with clinical laboratory values categorized as below, within, or above normal ranges will be tabulated showing change from baseline (shift tables) for each clinical laboratory analyte by study visit.

Laboratory values that are outside the normal range will also be flagged in the data listings and presented with the corresponding normal ranges. Any out-of-range values that are identified by the Investigator as being clinically significant will also be shown in a data listing.

#### **13.1.4.3 Vital Signs**

Descriptive summaries (mean, SD, median, minimum, and maximum) of actual values and changes from baseline will be calculated for systolic blood pressure, diastolic blood pressure, heart rate, respiratory rate, and body temperature.

The number of subjects with vital signs values categorized as below, within, or above normal ranges will be tabulated showing change from baseline (shift tables) for each parameter by study visit. Pre- and post-treatment values may also be presented with an analysis of mean changes from baseline.

#### **13.1.4.4 Twelve-lead Electrocardiograms**

The number and percentage of subjects with normal and abnormal ECG findings will be summarized for each time point. Abnormal results will be grouped as clinically significant and not clinically significant. A comparison of QT results will be presented. Summary statistics, for baseline values at Screening and each subsequent evaluation, will be displayed by treatment group for QT and the QT interval corrected for heart rate (QTc). In addition, the number and percent of subjects who experienced a change >30 ms or a change >60 ms will be presented.

Descriptive summaries (mean, SD, median, minimum, and maximum) will be presented for ECG measures of PR interval, QRS interval, QT interval, QTcF interval, and heart rate for each time point.

#### **13.1.4.5 Penn Physician Withdrawal Checklist**

Descriptive summaries (mean, SD, median, minimum, and maximum) will be presented for scores from the PWC-20 checklist, completed at Visits 14 and 15.

#### **13.1.4.6 Physical Examination Findings**

The number and percentage of subjects with normal and abnormal findings in the complete physical examination, including nasal passages examination, will be displayed.

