- c Physical examination will include measurement of weight and an examination of the nasal passages. Height will be measured at Screening and at Visit 14. The physical examinations done at Visit 1, Visit 2 and Visit 14 will be comprehensive. The physical examinations done at Visit 3 to Visit 13 will be focused but must include examination of the nasal passages and oropharynx. Other organ systems should be examined at Visit 3 to Visit 13 if the subject reports AEs or if the investigator has specific concerns.
- d [REDACTED].
- e 12-Lead electrocardiograms will be administered in a supine position after the subject has rested for 5 minutes.
- f For all subjects, a review of inclusion and exclusion criteria will be conducted at Visit 2 to confirm eligibility.

Note: Long-term C-SSRS will be administered at screening. All other C-SSRS evaluations will be "Since Last Visit."

Note: If central laboratory urine drug screen testing is positive for a subject [REDACTED], then the participation of the subject in the study may have to be discontinued. The Medical Monitor should be consulted on these cases. An unscheduled repeat urine drug screen may be obtained to investigate whether drug use is continuing.

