#### **10.2.4 Visit 15 (Follow-up, 54 weeks ±3 Days)**

At Visit 15, subjects should return to the study site and the following assessments will be completed:

- Measure vital signs after the subject has rested for 5 minutes: seated systolic and diastolic blood pressure, heart rate, respiratory rate, and body temperature (°F)
- Administer C-SSRS (Since Last Visit)
- Complete PWC-20
- Review and record AEs

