#### **11.2.1 Assessment**

The Investigator is responsible for the detection and documentation of events meeting the criteria and definition of an AE or SAE described previously. At each visit, the subject will be allowed time to spontaneously report any issues since the last visit or evaluation. The Investigator will then monitor and/or ask about or evaluate AEs using nonleading questions, such as

- “How are you feeling?”
- “Have you experienced any issues since your last visit?”
- “Have you taken any new medications since your last visit?”

Any clinically relevant observations made during the visit will also be considered AEs.

In addition, the Investigator will review the eDiary summary text for health problems and determine whether they are to be recorded in the EDC system as AEs.

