2.2. Study Endpoints

2.2.1. Safety Endpoints

The safety endpoints of this study include the following:

- Incidence and severity of AEs, AEs leading to discontinuation, and SAEs
- Changes in vital signs results
- Changes in clinical laboratory evaluation (hematology, chemistry, and urinalysis) results
- Changes in 12-lead ECG results
- Changes in physical examination findings
- Changes in HAM-D17 scores
- Changes in C-SSRS scores
- PWC-20 scores after termination of PH94B

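### Three safety displays that the protocol commits to are not specified in SAP 8 or the visible table index, and SAP 10 declares none of them removed

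*Protocol*

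**What the plan says.** The protocol uses firm wording for three safety displays.

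- **Physical examination (Protocol 13.1.4.6):** "The number and percentage of subjects with normal and abnormal findings in the complete physical examination, including nasal passages examination, will be displayed".
- **QT (Protocol 13.1.4.4):** after the QT and QTc summaries, "the number and percent of subjects who experienced a change >30 ms or a change >60 ms will be presented".
- **Vital signs (Protocol 13.1.4.3):** values below, within or above the normal range "will be tabulated showing change from baseline (shift tables) for each parameter by study visit".

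The Schedule of Events (Protocol 2.2, footnote c) shows which examinations are complete: "The physical examinations done at Visit 1, Visit 2 and Visit 14 will be comprehensive". Protocol 13.1 leaves the comprehensive description of the analyses to the SAP.

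SAP 2.2.1 keeps "Changes in physical examination findings" as a safety endpoint, and the opening of SAP 8 names physical and nasal examination among the safety data. SAP 6.1.8 sends data with no planned analysis to listings only. SAP 10 is the place where departures from the planned analysis are declared.

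For the withdrawal checklist, Protocol 13.1.4.5 plans summaries of "scores from the PWC-20 checklist, completed at Visits 14 and 15". SAP 8.7 restricts the analysis to subjects who completed Visits 14 and 15, but then names Visit 1 and Visit 15 as the visits to be presented.

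**The concern.** Safety is the primary objective. The study has no comparator and no data safety monitoring board, and SAP 10 removes the interim safety analysis, so the final descriptive summaries carry the evidence. A programmer who follows SAP 8 and the visible index would produce no normal/abnormal percentages for the complete examination, no counts above the 30 and 60 ms thresholds, and no vital-sign shift tables. A reader of the report would find nothing in SAP 10 to explain why.

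The nasal examination is the most relevant of these. The product is intranasal, Protocol 7.2 gives that route as the reason for examining the nasal passages, and Protocol 5.3 warns of local reactions in the nose.

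**Working it through.** No sample size, power or event figure is involved, so the check sets the passages side by side and counts.

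| Display | Protocol | SAP 8 text | SAP 12 summary table | Listing | Named as removed in SAP 10? |
|---|---|---|---|---|---|
| Complete physical and nasal examination, n and % normal/abnormal | 13.1.4.6, firm | Named in the opening of SAP 8; no subsection in 8.1 to 8.9 | None visible in 12.3 or 12.4 | 16.2.9.3 | No |
| n and % with a change above 30 or 60 ms | 13.1.4.4, firm | 8.4: comparison and summary statistics for QT and QTcF; change from baseline named only for PR, QRS and heart rate | 14.3.6.2.3; title shows no change categories | 16.2.9.2 | No |
| Vital-sign shift tables | 13.1.4.3, firm | 8.3: observed values and change only | 14.3.6.1; observed values and change only | 16.2.9.1 | No |

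**Displays.** Promised in the protocol: 3. Specified in SAP 8 or the visible index: 0. Named as removed in SAP 10: 0.

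**Endpoints.** SAP 2.2.1 lists 8 safety endpoints. Seven have a subsection in SAP 8: adverse events (8.1), laboratory (8.2), vital signs (8.3), ECG (8.4), C-SSRS (8.6), PWC-20 (8.7) and HAM-D (8.8). So 8 − 7 = 1 has none: physical examination. ECG and vital signs have a subsection and a table, but each lacks a display that the protocol promised.

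**Could general SAP text supply the displays?** SAP 6.1.7.1 (General) defines a shift from baseline for an unnamed parameter, which would suit vital signs. No section or visible table applies it to them, whereas SAP 8.2 expressly asks for shift tables for laboratory analytes. Under SAP 6.1.8, unassigned data go to listings.

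**Does SAP 10 cover the omissions?** It names the eDiary-based objectives and the interim analysis. A further line refers to endpoints removed because data were not collected, but identifies none. It does not fit here: the SAP schedule has vital signs, ECG and physical examination at every visit from 1 to 14, and listings are planned for all three. The protocol also measures "seated systolic and diastolic blood pressure, heart rate, respiratory rate, and body temperature" at Visit 15. The sentence about a qualitative review replacing change in proportion matches the CGI and PGI-C endpoints in SAP 2.2.2 and names none of these displays.

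**PWC-20.** Both schedules place it at Visit 14/ET and Visit 15 only. Visit 1 in SAP 8.7 therefore contradicts the schedules and the preceding sentence of the same section.

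**The case against.** The strongest reply is that much of the SAP was not available. The contents list table shells from page 35 and listing shells from page 70 of a 99-page document, and the text supplied ends with the listing index. The shell for Table 14.3.6.2.3 could contain threshold rows. The index skips Table 14.3.6.3, which would fall between ECG and concomitant medications, the place that physical examination holds among the listings. Two ECG tables share one title, no Section 9 appears, and the efficacy part of the index is empty although SAP 7.5 plans efficacy summaries. All of this stands. A reader might infer that the displays are absent from the SAP altogether; the documents do not support that. What is shown is that SAP 8 and the visible index do not specify them.

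A reader might also infer that every complete examination would appear in a listing only. That is not established for Visit 2: Protocol 13.1.2.3 counts physical examination findings among the baseline characteristics, and SAP 7.3 and Table 14.1.2.1 summarise baseline characteristics, although neither itemises the examination.

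The third reply is that little is lost. Much of this also stands. The displays are descriptive, and the counts could be derived from the listings. Protocol 11.2.1 says: "Any clinically relevant observations made during the visit will also be considered AEs". Abnormal ECGs receive a second expert evaluation (Protocol 10.3.1.2.2), and SAP 8.4 keeps the percentage of abnormal ECGs by clinical significance. SAP 8.3 keeps observed values and changes. What remains uncovered is mainly examination findings that are not recorded as adverse events, nasal findings among them, and the protocol's own threshold counts.

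**Conclusion.** The point holds for SAP 8 and the visible index. Three of three promised displays are not specified and not declared as removed, and 1 of 8 safety endpoints has no specified summary. The PWC-20 visit label is a plain slip. The conclusion assumes that the unseen shells and any Table 14.3.6.3 do not hold the displays. If they do, what remains is that SAP 8 and the index should name them.

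The practical consequence is limited, because the data are collected and listed and the related summaries survive. It is still worth correcting: the displays serve the primary objective, and the protocol and SAP otherwise disagree without explanation.

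Two gaps lie in the protocol itself. It does not say whether the 30 and 60 ms thresholds apply to QT or to QTc, and neither document gives normal ranges for vital signs.

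**What to change.** - **SAP 8 and 12.3:** add a table of n and % normal/abnormal for the complete physical examination, including nasal passages, at Visit 2 and Visit 14/ET. Tabulating the focused examinations at Visits 3 to 13 is optional and goes beyond the protocol's promise.
- **SAP 8.4 and Table 14.3.6.2.3:** add change from baseline for QT and QTcF and the n and % of subjects with a change above 30 and above 60 ms. State which interval the thresholds apply to, for example QTcF, which the SAP already derives.
- **SAP 8.3:** apply the shift definition in SAP 6.1.7.1 to the five vital-sign parameters with stated normal ranges, or declare and justify the removal in SAP 10.
- **SAP 8.7:** change Visit 1 to Visit 14.
- If the shells already hold any of these displays, name them in SAP 8 and the index instead.

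The cost is SAP wording, a few extra tables from data already collected, and agreement on vital-sign normal ranges. No visit or assessment is added.

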### 13.1.5 Efficacy Analysis

Efficacy variables will be summarized and analyzed using the safety population.

#### 13.1.5.1 Exploratory Endpoints

Overall subject improvement as assessed by the clinician's rating on LSAS, CGI-S, CGI-I, and the subject's rating of the PGI-C from Screening (Visit 1) through Follow-up (Visit 15) will be summarized, including changes from baseline where appropriate. The change in LSAS, CGI-I, and PGI-C scores from Baseline to Visit 14 may also be explored using generalized linear model for repeated measures.

In addition, overall change in the pattern in the frequency of PH94B use (frequent users; 3 or 4 times a day and less frequent users;  $\leq$  2 times a day), change in medication use as documented by the clinician and the subject between Screening (Visit 1) and Follow-up (Visit 15) will be summarized.

Full details on this exploratory analysis will be provided in the SAP.

The exploratory endpoints are as follows:

- Change in total LSAS scores over time with use of PH94B
- Change in proportion of subjects with CGI-S scores  $>4$  over time with use of PH94B
- Change in proportion of subjects with CGI-I scores of 1 (Very much improved) or 2 (Much improved) over time with use of PH94B
- Change in proportion of subjects with PGI-C scores of 1 (Very much improved) or 2 (Much improved) over time with use of PH94B
- [REDACTED]
- [REDACTED]
- [REDACTED]

### 13.1.6 Interim Analysis

Data cuts for interim data summaries are planned to support regulatory filings. An interim safety analysis will be performed when approximately 100 subjects have completed 12 months of PH94B dosing up to 4 times per day and approximately 300 subjects have completed 6 months of PH94B dosing up to 4 times per day. The study will remain ongoing until the last subject has been discontinued from the study and the database has been locked.

## 13.2. Sample Size Determination

Based on feedback from the FDA, the sample size for this study (up to 600 subjects) has been selected to attain a PH94B safety database per the ICH E1 Guideline.

## 14. STUDY CONDUCT

Steps to ensure the accuracy and reliability of data include the selection of qualified investigators and appropriate study sites, review of protocol procedures with the Investigator and associated personnel before the study, periodic monitoring visits, and meticulous data management.

### 14.1. Sponsor and Investigator Responsibilities

#### 14.1.1 Sponsor Responsibilities

The sponsor is obligated to conduct the study in accordance with strict ethical principles (Section 16). The sponsor reserves the right to withdraw a subject from the study (Section 8.3), to terminate participation of a study site at any time (Section 14.7), and/or to discontinue the study (Section 14.6).

VistaGen Therapeutics, Inc. agrees to provide the Investigator with sufficient material and support to permit the Investigator to conduct the study according to the study protocol.

#### 14.1.2 Investigator Responsibilities

By signing the Investigator's Agreement (Section 18.1), the Investigator indicates that he or she has read the protocol carefully, fully understands the requirements, and agrees to conduct the study in accordance with the procedures and requirements described in this protocol.

The study will be conducted in accordance with ICH GCP and applicable United States Code of Federal Regulations (CFR). The Principal Investigator will assure that no deviation from, or changes to, the protocol will take place without prior agreement from the Investigational New Drug (IND) sponsor, funding agency and documented approval from the IRB, except where necessary to eliminate an immediate hazard(s) to the study subjects. All personnel involved in the conduct of this study have completed Human Subjects Protection and ICH GCP training.

Investigators should ensure that all persons who are delegated study-related responsibilities are adequately qualified and informed about the protocol, the IP(s), and their specific duties within the context of the study. Investigators are responsible for providing VistaGen Therapeutics, Inc. with documentation of the qualifications, GCP training, and research experience for themselves and their staff as required by the sponsor and the relevant governing authorities.

To ensure compliance with the guidelines, the study may be audited by an independent person. The Investigator agrees, by written consent to this protocol, to cooperate fully with compliance checks by allowing access to all study documentation by authorized individuals.

#### 14.1.3 Confidentiality and Privacy

Subject confidentiality and privacy are strictly held in trust by the participating investigators, their staff, and the sponsor and their staff. This confidentiality is extended to cover testing of biological samples and genetic tests in addition to the clinical information relating to subjects. Therefore, the study protocol, documentation, data, and all other information generated will be held in strict confidence. No information concerning the study or the data will be released to any unauthorized third party without prior written approval of the sponsor.

All research activities will be conducted in as private a setting as possible.

The study monitor, other authorized representatives of the sponsor, representatives of the IRB, regulatory agencies, or pharmaceutical company supplying study product may inspect all

documents and records required to be maintained by the Investigator, including, but not limited to, medical records (office, clinic, or hospital) and pharmacy records for the subjects in this study. The clinical study site will permit access to such records.

The study subject's contact information will be securely stored at each clinical site for internal use during the study. At the end of the study, all records will continue to be kept in a secure location for as long a period as dictated by the reviewing IRB, institutional policies, or sponsor requirements.

Study subject research data, which is for purposes of statistical analysis and scientific reporting, will be transmitted to and stored at [REDACTED]. This will not include the subject's contact or identifying information. Rather, individual subjects and their research data will be identified by a unique study identification number. The study data entry and study management systems used by clinical sites and by [REDACTED] staff will be secured and password protected. At the end of the study, all study databases will be de-identified and archived at [REDACTED].

#### **14.2. Site Initiation**

Study personnel may not screen or enroll subjects into the study until after receiving notification from the sponsor or its designee that the study can be initiated at the study site. The study site will not be authorized for study initiation until:

1. The study site has received the appropriate IRB approval for the protocol and the appropriate ICF.
2. All regulatory documents have been submitted to and approved by the sponsor or its designee.
3. The study site has a Clinical Trial Agreement in place.
4. Study site personnel, including the Investigator, have participated in a study initiation meeting.

#### **14.3. Screen Failures**

Subjects who fail inclusion and/or exclusion criteria may be rescreened for the study on a case-by-case basis after discussion with the medical monitor. Subjects may only be rescreened once 30 days or more after the original Screening visit. If a subject is eligible to enter the study after having previously failed screening, the subject will be assigned a new subject identification number.

Screen failures are defined as subjects who consent to participate in the clinical study but are not subsequently entered in the study. A minimal set of screen failure information is required to ensure transparent reporting of screen failure subjects to meet the Consolidated Standards of Reporting Trials (CONSORT) publishing requirements and to respond to queries from regulatory authorities. Minimal information includes demography, screen failure details, eligibility criteria, and any SAE.

#### **14.4. Study Documents**

All documentation and material provided by VistaGen Therapeutics, Inc. for this study is to be retained in a secure location and treated as confidential material.

#### **14.4.1 Informed Consent**

Informed consent forms describing in detail the study intervention, study procedures, and risks are given to the subject and written documentation of informed consent is required prior to starting intervention/administering study intervention.

Informed consent is a process that is initiated prior to the individual's agreeing to participate in the study and continues throughout the individual's study participation. Consent forms will be IRB approved and the subject will be asked to read and review the document. The Investigator will explain the research study to the subject and answer any questions that may arise. A verbal explanation will be provided in terms suited to the subject's comprehension of the purposes, procedures, and potential risks of the study and of their rights as research participants. Subjects will have the opportunity to carefully review the written ICF and ask questions prior to signing. The subject should have the opportunity to discuss the study with their family or surrogates or think about it prior to agreeing to participate. The subject will sign the informed consent document prior to any procedures being done specifically for the study. Subjects must be informed that participation is voluntary and that they may withdraw from the study at any time, without prejudice. A copy of the ICF will be given to the subjects for their records. The informed consent process will be conducted and documented in the source document (including the date) and the ICF signed before the subject undergoes any study-specific procedures. The rights and welfare of the subjects will be protected by emphasizing to them that the quality of their medical care will not be adversely affected if they decline to participate in this study.

